**Table 51 Exercise Advice (EA) -compliance information randomised patients (ITT) by treatment**

Exercise Advice - Non-Set Centre	Treatment  : NMES + EA and NMES+EA+SET N=(XX)	Control  : EA and EA+SET N=(XX)	Total N=(XX)
Total weeks of exercises reported			
mean (SD)	XX.XX (XX.XX)	XX.XX (XX.XX)	XX.XX (XX.XX)
median (IQR)	XX.XX (XX.XX, XX.XX)	XX.XX (XX.XX, XX.XX)	XX.XX (XX.XX, XX.XX)
Total minutes of exercised at home			
mean (SD)	XX.XX (XX.XX)	XX.XX (XX.XX)	XX.XX (XX.XX)
median (IQR)	XX.XX (XX.XX, XX.XX)	XX.XX (XX.XX, XX.XX)	XX.XX (XX.XX, XX.XX)
Average minutes of exercise at home at week			
mean (SD)	XX.XX (XX.XX)	XX.XX (XX.XX)	XX.XX (XX.XX)
median (IQR)	XX.XX (XX.XX, XX.XX)	XX.XX (XX.XX, XX.XX)	XX.XX (XX.XX, XX.XX)

**Table 52 Summary table of Device use questionnaire**

Variable	Value
N	N = (XX)
Overall, how easy did you find the device to use	
1 Very easy	XX (XX.X%)
2	XX (XX.X%)
3	XX (XX.X%)
4	XX (XX.X%)
5 Very difficult	XX (XX.X%)
Do you think the device helped to lessen the pain in your legs	
1-Yes, a lot	XX (XX.X%)
2	XX (XX.X%)
3	XX (XX.X%)
4	XX (XX.X%)
5-Not at all	XX (XX.X%)
Do you think you can walk further	
Yes	XX (XX.X%)
No	XX (XX.X%)
No change	XX (XX.X%)
Did you use the device as instructed	
Yes	XX (XX.X%)
No	XX (XX.X%)
Do you think you could have used the device more often than you did?	
Yes	XX (XX.X%)
No	XX (XX.X%)
Did you use the device beyond the 3 months treatment	
1-Yes, a lot	XX (XX.X%)
2	XX (XX.X%)
3	XX (XX.X%)
4	XX (XX.X%)
5-Not at all	XX (XX.X%)

## 8.9.7 Subgroup

### 8.9.7.1 Baseline characteristics by Subgroups

**Table 53 Summary of baseline characteristics of randomised patients (ITT) by Subgroups**

Variable	EA N=(XX)	EA+NMES N=(XX)	EA+SET N=(XX)	EA+SET+NMES N=(XX)	Total N=(XX)
Age					
mean (SD)	XX.XX (XX.XX)	XX.XX (XX.XX)	XX.XX (XX.XX)	XX.XX (XX.XX)	XX.XX (XX.XX)
median (IQR)	XX.XX (XX.XX, XX.XX)	XX.XX (XX.XX, XX.XX)	XX.XX (XX.XX, XX.XX)	XX.XX (XX.XX, XX.XX)	XX.XX (XX.XX, XX.XX)
Sex N(%)					
Female	XX (XX.X%)	XX (XX.X%)	XX (XX.X%)	XX (XX.X%)	XX (XX.X%)
Male	XX (XX.X%)	XX (XX.X%)	XX (XX.X%)	XX (XX.X%)	XX (XX.X%)
Ethnicity N(%)					
Asian	XX (XX.X%)	XX (XX.X%)	XX (XX.X%)	XX (XX.X%)	XX (XX.X%)
Black	XX (XX.X%)	XX (XX.X%)	XX (XX.X%)	XX (XX.X%)	XX (XX.X%)
Mixed	XX (XX.X%)	XX (XX.X%)	XX (XX.X%)	XX (XX.X%)	XX (XX.X%)
White	XX (XX.X%)	XX (XX.X%)	XX (XX.X%)	XX (XX.X%)	XX (XX.X%)
Work status N(%)					
Higher managerial and professional occupations	XX (XX.X%)	XX (XX.X%)	XX (XX.X%)	XX (XX.X%)	XX (XX.X%)
Intermediate occupations (e.g. clerical, sales, service)	XX (XX.X%)	XX (XX.X%)	XX (XX.X%)	XX (XX.X%)	XX (XX.X%)
Lower managerial and professional occupations	XX (XX.X%)	XX (XX.X%)	XX (XX.X%)	XX (XX.X%)	XX (XX.X%)
Lower supervisory and technical occupations	XX (XX.X%)	XX (XX.X%)	XX (XX.X%)	XX (XX.X%)	XX (XX.X%)
Never worked or long-term unemployed	XX (XX.X%)	XX (XX.X%)	XX (XX.X%)	XX (XX.X%)	XX (XX.X%)
Routine occupations	XX (XX.X%)	XX (XX.X%)	XX (XX.X%)	XX (XX.X%)	XX (XX.X%)
Semi-routine occupations	XX (XX.X%)	XX (XX.X%)	XX (XX.X%)	XX (XX.X%)	XX (XX.X%)
Small employers and own account workers	XX (XX.X%)	XX (XX.X%)	XX (XX.X%)	XX (XX.X%)	XX (XX.X%)
Retired N(%)					
No	XX (XX.X%)	XX (XX.X%)	XX (XX.X%)	XX (XX.X%)	XX (XX.X%)
Yes	XX (XX.X%)	XX (XX.X%)	XX (XX.X%)	XX (XX.X%)	XX (XX.X%)
Performance limited due to IC (N%)					
A little	XX (XX.X%)	XX (XX.X%)	XX (XX.X%)	XX (XX.X%)	XX (XX.X%)
A lot	XX (XX.X%)	XX (XX.X%)	XX (XX.X%)	XX (XX.X%)	XX (XX.X%)
Not at all	XX (XX.X%)	XX (XX.X%)	XX (XX.X%)	XX (XX.X%)	XX (XX.X%)

Imperial Clinical Trials Unit	STATISTICAL ANALYSIS PLAN	NESIC
-------------------------------	---------------------------	-------

**Table 54 Summary of Medical History of randomised patients (ITT) by Subgroups**

**Table 55 Summary of Medication list of randomised patients (ITT) by Subgroups**

**Table 56 Summary of Vital Signs of randomised patients (ITT) by Subgroups**

**Table 57 Summary of Lifestyle History of randomised patients (ITT) by Subgroups**

**Table 58 Summary of Treadmill test of randomised patients (ITT) by Subgroups**

#### 8.9.7.2 Derivative variables by Subgroups

**Table 59 Summary of ICQ and EQ5D-5L Quality of Life scores of randomised patients (ITT) by Subgroups**

**Table 60 Summary SF-36 of Quality of Life scores of randomised patients (ITT) by Subgroups**

**Table 61 Summary of Compliance of randomised patients (ITT) by Subgroups**

#### 8.9.7.3 Subgroups Analysis

**Table 62 Summary of AWD by Visit and for SET vs Non-SET (subgroup1)**

Visit	Subgroup	N	Mean	SD	Median	Min	Max
Baseline							
	Treatment  : NMES + EA and NMES+EA+SET	XX	XX.XX	XX.XX	XX	XX	XX
	Control  : EA and EA+SET	XX	XX.XX	XX.XX	XX	XX	XX
3 mths							
	Treatment  : NMES + EA and NMES+EA+SET	XX	XX.XX	XX.XX	XX	XX	XX
	Control  : EA and EA+SET	XX	XX.XX	XX.XX	XX	XX	XX

Treatment: NMES + Local Available Exercise Therapy (NMES+EA and NMES+EA+SET)

Control: Local Available Exercise Therapy (EA and EA+SET)

**Table 63 Output of Tobit Regression Model to assess the effects of SET vs non-SET (subgroup1) for AWD at 3 months**

Variable	Coefficient	SE	t	Confidence		
				P> t	interval	
AWD(Baseline)	XX.XX	XX.XX	X.XX	X.XXX	X.XX	X.XX
Treatment	XX.XX	XX.XX	X.XX	X.XXX	X.XX	X.XX
Centre	XX.XX	XX.XX	X.XX	X.XXX	X.XX	X.XX
Group	XX.XX	XX.XX	X.XX	X.XXX	X.XX	X.XX
_cons	XX.XX	XX.XX	X.XX	X.XXX	X.XX	X.XX
/sigma	XX.XX	XX.XX			X.XX	X.XX
Obs. Summary:	XX left-censored observations					
	XX uncensored observations					
	XX right-censored observations at (...) dependent variable					

Tobit Regression Model: AWD at 3 months = intercept + AWD (baseline)+ Treatment + Centre + Group + residual error.

Treatment=NMES + local available Exercise therapy vs. local available Exercise therapy only (1,0), Centre=Centre identifier and Group=Set or non-SET group (1,0).

**Table 64 Chi square test of Improvement of >60 m in AWD at three months between SET and Non-SET (subgroup1)**

Improvement of >60 m in the AWD at 3 months	NMES + Local available exercise therapy N=(XX)	Local available exercises therapy N=(XX)	Total	
			N=(XX)	N=(XX)
Yes	XX (XX.X%)	XX (XX.X%)	XX (XX.X%)	XX (XX.X%)
No	XX (XX.X%)	XX (XX.X%)	XX (XX.X%)	XX (XX.X%)

Imperial Clinical Trials Unit	STATISTICAL ANALYSIS PLAN	NESIC
-------------------------------	---------------------------	-------

**Table 65 Chi square test of Improvement of >100 m in AWD at three months between SET and Non-SET (subgroup1).** Same display as Table 64, but for improvement of >100 m in AWD and subgroup1.

**Table 66 Summary of AWD by Visit and for NMES+SET+EA vs SET+EA (subgroup2).** Same display as Table 62, but for subgroup2.

**Table 67 Output of Tobit Regression Model to assess the effects of NMES+SET + EA vs SET+ EA (subgroup2) for AWD at 3 months.** Same display as Table 63, but for subgroup2. Tobit Regression Model: AWD at 3 months = intercept + AWD (baseline)+ Treatment + Centre + Group + residual error. Treatment=NMES + local available Exercise therapy vs. local available Exercise therapy only (1,0), Centre=Centre identifier and Group= Set or non-SET group (1,0). Subgroup2: NMES+SET+EA vs SET+EA.

**Table 68 Chi square test of Improvement of >60 m in AWD at three months between NMES+SET + EA and SET+ EA (subgroup2).** Same display as Table 64, but for improvement of >100 m in AWD and subgroup2.

**Table 69 Chi square test of Improvement of >100 m in AWD at three months between NMES+SET + EA and SET+ EA (subgroup2).** Same display as Table 64, but for improvement of >100 m in AWD and subgroup2.

**Table 70 Summary of AWD by Visit and for NMES+EA vs EA (subgroup3).** Same display as Table 62, but for subgroup3.

**Table 71 Output of Tobit regression model to assess the effects of NMES+EA vs EA (subgroup3) for AWD at 3 months.** Same display as Table 63, but for subgroup3. Tobit Regression Model: AWD at 3 months = intercept + AWD (baseline)+ Treatment + Centre+ Group + residual error. Treatment=NMES + local available Exercise therapy vs. local available Exercise therapy only (1,0), Centre=Centre identifier and Group= Set or non-SET group (1,0). Subgroup3: NMES in the non-SET (NMES+EA vs EA).

**Table 72 Chi square test of Improvement of >60 m in AWD at three months between NMES+EA and EA (subgroup3).** Same display as Table 64, but for improvement of >60 m in AWD and subgroup3.

**Table 73 Chi square test of Improvement of >100 m in AWD at three months between NMES+EA and EA (subgroup3).** Same display as Table 64, but for improvement of >100 m in AWD and subgroup3.

**Table 74 Summary of AWD by Visit and for NMES+EA vs SET+EA (subgroup4).** Same display as Table 62, but for subgroup4.

**Table 75 Output of Tobit regression model to assess the effects of NMES+EA vs SET+EA (subgroup4) for AWD3M.** Same display as Table 63, but for subgroup4 Tobit Regression Model: AWD at 3 months = intercept + AWD (baseline)+ Treatment + Centre+ Group + residual error. Treatment=NMES + local available Exercise therapy vs. local available Exercise therapy only (1,0), Centre=Centre identifier and Group= Set or non-SET group (1,0). Subgroup4: NMES+EA vs SET +EA.

**Table 76 Chi square test of Improvement of >60 m in AWD at three months between NMES+EA and SET+EA (subgroup4).** Same display as Table 64, but for improvement of >60 m in AWD and subgroup4.

**Table 77 Chi square test of Improvement of >100 m in AWD at three months between NMES+EA and SET+EA (subgroup4).** Same display as Table 64, but for improvement of >100 m in AWD and subgroup4.

**Table 78 Summary of AWD by Visit and for NMES+SET+EA vs NMES+EA (subgroup5).** Same display as Table 62, but for subgroup5.

**Table 79 Output of Tobit regression model to assess the effects of NMES+SET+EA vs NMES+EA (subgroup5) for AWD3M.** Same display as Table 63, but for subgroup5. Tobit Regression Model: AWD at 3 months = intercept + AWD (baseline)+ Treatment + Centre+ Group + residual error. Treatment=NMES + local available Exercise therapy vs. local available Exercise therapy only (1,0), Centre=Centre identifier and Group= Set or non-SET group (1,0). Subgroup5: NMES+SET+EA vs NMES+EA.

Imperial Clinical Trials Unit	STATISTICAL ANALYSIS PLAN	NESIC
-------------------------------	---------------------------	-------

**Table 80 Chi square test of Improvement of >60 m in AWD at three months between NMES+SET+EA and NMES+EA (subgroup5).** Same display as Table 64, but for improvement of >60 m in AWD and subgroup5.

**Table 81 Chi square test of Improvement of >100 m in AWD at three months between NMES+SET+EA and NMES+EA (subgroup5).** Same display as Table 64, but for improvement of >100 m in AWD and subgroup5.

### 8.9.8 Safety Analysis

**Table 82 Summary of Adverse Events by treatment**

Variable	Treatment  : NMES + EA and NMES+EA+SET	Control  : EA and EA+SET	Total N=(XX)
	N=(XX)	N=(XX)	
Severity			
Mild	XX (XX.X%)	XX (XX.X%)	XX (XX.X%)
Moderate	XX (XX.X%)	XX (XX.X%)	XX (XX.X%)
Severe	XX (XX.X%)	XX (XX.X%)	XX (XX.X%)
Life threatening or disabling	XX (XX.X%)	XX (XX.X%)	XX (XX.X%)
Fatal	XX (XX.X%)	XX (XX.X%)	XX (XX.X%)
Relationship Study device			
Definitely	XX (XX.X%)	XX (XX.X%)	XX (XX.X%)
Probably	XX (XX.X%)	XX (XX.X%)	XX (XX.X%)
Possibly	XX (XX.X%)	XX (XX.X%)	XX (XX.X%)
Unlikely	XX (XX.X%)	XX (XX.X%)	XX (XX.X%)
Not related	XX (XX.X%)	XX (XX.X%)	XX (XX.X%)
Not assessable	XX (XX.X%)	XX (XX.X%)	XX (XX.X%)
Site name			
Cambridge University Hospital	XX (XX.X%)	XX (XX.X%)	XX (XX.X%)
Dorset County Hospital	XX (XX.X%)	XX (XX.X%)	XX (XX.X%)
Hull and East Yorkshire Hospitals	XX (XX.X%)	XX (XX.X%)	XX (XX.X%)
Imperial College Healthcare	XX (XX.X%)	XX (XX.X%)	XX (XX.X%)
Newcastle Upon Tyne Hospitals	XX (XX.X%)	XX (XX.X%)	XX (XX.X%)
North Bristol	XX (XX.X%)	XX (XX.X%)	XX (XX.X%)
Nottingham University Hospitals	XX (XX.X%)	XX (XX.X%)	XX (XX.X%)
Royal Bournemouth & Christchurch Hospital	XX (XX.X%)	XX (XX.X%)	XX (XX.X%)
St George's University Hospitals	XX (XX.X%)	XX (XX.X%)	XX (XX.X%)
Taunton & Somerset	XX (XX.X%)	XX (XX.X%)	XX (XX.X%)
University Hospital Southampton	XX (XX.X%)	XX (XX.X%)	XX (XX.X%)

 Treatment: NMES + Local Available Exercise Therapy (NMES+EA and NMES+EA+SET)

 Control: Local Available Exercise Therapy (EA and EA+SET)

**Table 83 Summary of Serious Adverse Events by treatment**

Variable N(%)	Treatment  : NMES + EA and NMES+EA+SET N=(XX)	Control  : EA and EA+SET N=(XX)	Total N=(XX)
Severity			
Mild	XX (XX.X%)	XX (XX.X%)	XX (XX.X%)
Moderate	XX (XX.X%)	XX (XX.X%)	XX (XX.X%)
Severe	XX (XX.X%)	XX (XX.X%)	XX (XX.X%)
Life threatening or disabling	XX (XX.X%)	XX (XX.X%)	XX (XX.X%)
Fatal	XX (XX.X%)	XX (XX.X%)	XX (XX.X%)
Outcome			
Recovered	XX (XX.X%)	XX (XX.X%)	XX (XX.X%)
Recovering/Improving	XX (XX.X%)	XX (XX.X%)	XX (XX.X%)
Not recovered	XX (XX.X%)	XX (XX.X%)	XX (XX.X%)
Fatal	XX (XX.X%)	XX (XX.X%)	XX (XX.X%)
Not assessable	XX (XX.X%)	XX (XX.X%)	XX (XX.X%)
Causal Relationship to device			
Definitely	XX (XX.X%)	XX (XX.X%)	XX (XX.X%)
Probably	XX (XX.X%)	XX (XX.X%)	XX (XX.X%)
Possibly	XX (XX.X%)	XX (XX.X%)	XX (XX.X%)
Unlikely	XX (XX.X%)	XX (XX.X%)	XX (XX.X%)
Not related	XX (XX.X%)	XX (XX.X%)	XX (XX.X%)
Not assessable	XX (XX.X%)	XX (XX.X%)	XX (XX.X%)
Site Name			
Cambridge University Hospital	XX (XX.X%)	XX (XX.X%)	XX (XX.X%)
Dorset County Hospital	XX (XX.X%)	XX (XX.X%)	XX (XX.X%)
Hull and East Yorkshire Hospitals	XX (XX.X%)	XX (XX.X%)	XX (XX.X%)
Imperial College Healthcare	XX (XX.X%)	XX (XX.X%)	XX (XX.X%)
Newcastle Upon Tyne Hospitals	XX (XX.X%)	XX (XX.X%)	XX (XX.X%)
North Bristol	XX (XX.X%)	XX (XX.X%)	XX (XX.X%)
Nottingham University Hospitals	XX (XX.X%)	XX (XX.X%)	XX (XX.X%)
Royal Bournemouth & Christchurch	XX (XX.X%)	XX (XX.X%)	XX (XX.X%)
Hospital			
St George's University Hospitals	XX (XX.X%)	XX (XX.X%)	XX (XX.X%)
Taunton & Somerset	XX (XX.X%)	XX (XX.X%)	XX (XX.X%)
University Hospital Southampton	XX (XX.X%)	XX (XX.X%)	XX (XX.X%)

Treatment: NMES + Local Available Exercise Therapy (NMES+EA and NMES+EA+SET)Control: Local Available Exercise Therapy (EA and EA+SET)

Imperial Clinical Trials Unit	STATISTICAL ANALYSIS PLAN	NESIC
-------------------------------	---------------------------	-------

**Table 84 List of all Adverse Events**

Subject id	Site Name	Adverse Description	Event	Frequency	Severity	Relationship device	Study	Treatment of Event	Outcome	SAE Classification	Reason	Treatment

**Table 85 List of all Serious Adverse Events**

Same display as Table 84, but for SAEs.

**Table 86 Summary of Concomitant Medications**

Same display as Table 83, but for Concomitant Medications.

**Table 87 List of all Concomitant Medications**

Same display as Table 84, but for Concomitant Medications.

## 8.10 Figures to present

- Figure 1 Time trend of EQ5D: Health Score;
- Figure 3 Time trend of SF-36 in the treatments (all the scores)
- Figure 4 Time trend of ICQ score in the treatments
- Figure 5 Forest Plot of all Sub-Groups Analysis

## 9. Data Monitoring and Ethics Committee (DMEC)

In line with current NIHR recommendations a Data Monitoring Committee (DMC) will be convened and will include as a minimum a clinician with experience in the relevant area and an expert trial statistician.

The role of the DMC is to monitor patient safety and treatment efficacy data. Details of membership, responsibilities and frequency of meetings will be conducted as per the EME research governance guidelines and are defined in a separate DMC Charter. A DMC meeting will be held prior to the first patient's first visit, following completion of an internal pilot study and will then be held one month prior to each TSC meeting.

The independent Data Monitoring Committee (DMC) meeting will be scheduled yearly, with possible reviews every 6 months.

## 13. Appendices

### 13.1 Appendix 1- Treatments

#### 13.1.1 Supervised Exercise Program (SET)

The supervised exercise program (SET) is not standardised among the centres. The table below shows the differences, both in the frequency of sessions as well as total length of the program.

**Table A1. Overview of the Program Information by Centre (target SET per centre)**

SET Centre	Number of sessions per week (target)	Program duration by months	Total number of sessions
*Imperial College Healthcare	1	6	24
North Bristol	2	3	24
Hull and East Yorkshire Hospitals	3	3	36
University Hospital Southampton	1	2	8
Dorset County Hospital	1	2	8
Royal Bournemouth & Christchurch Hospital	1	3	12

\*Imperial SET classes typically last 6 months so extra classes beyond 3 months will be entered under unscheduled visit

#### 13.1.2 Neuromuscular electrical stimulation device (NMES)

The table below shows the summary of the recommended uses of NMES

**Table A2 Overview of the Neuromuscular electrical stimulation device (NMES)**

Minutes for session	Sessions per week	Number of weeks	Total of sessions	Total minutes
30	7	12	84	2520

#### 13.1.3 Exercise Advice (EA)

The Exercise Advice (EA) is not standardised among the centres. The table below shows an example of recommended guidelines.

**Table A3 Overview of the Exercise Advice (EA)**

Centre	Weeks	Instructions	Min of exercise per week 	Total min
Imperial College Healthcare	12	3 times a week	90	1080
University Hospital Southampton	12	3 - 5 times a week	90 - 150	1080 - 1800
Royal Bournemouth & Christchurch Hospital	12	5 times a week	150	1800
Taunton & Somerset	12	3 times a week	90	1080
Cambridge University Hospital	12	5 times a week	150	1800
Dorset County Hospital	12	3 times a week	90	1080
Hull and East Yorkshire Hospitals 	12			
Newcastle Upon Tyne Hospital	12	3 times a week	90	1080
North Bristol	12	3 times a week	90	1080
Nottingham University Hospital	12	7 times a week	210	2520

Patients are advised on the type of exercise but with no specification as to duration and frequency of exercise.

The minimum of exercise per week was estimated assuming the advice patients were given to exercise at least 30 minutes per session.

## 13.2 Appendix 2 - Formulas for Derived Variables

### 13.2.1 Intermittent Claudication Score (IC)

The IC score will be calculated using the answers provided by the patients recorded according to the Intermittent Claudication Questionnaire. This information is collected at baseline, 3, 6 and 12 months.

The Individual Intermittent Claudication Score is obtained by adding all the points assigned in each question and scaling to 100 (where the maximum score of 80 is represented as 100). [13]

**Table A4 The intermittent Claudication Questionnaire – Question scores**

Answers for question 1	Score	Answers for questions 2 -8	Score
None, I had no leg pain	0	Not limited at all	0
Very mild	1	A little limited	1.25
Mild	2	Moderately limited	2.5
Severe	3	Very limited	3.75
Moderate	4	Totally limited	5
Very severe	5		
Answers for question 9	Score	Answers for questions 10-16	Score
Not at all	0	None of the time	0
Less than once a week	1.25	A little of the time	1.25
Once a day	2.5	Some of the time	2.5
2 to 3 times a day	3.75	Most of the time	3.75
More than 3 times a day	5	All of the time	5

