### **7.4 Secondary Endpoint variables**

- Initial claudication distance (ICD) at baseline, 3, 6 and 12 months.
 

For participants that walked more than 15 minutes, their ICD will be censored at 15 minutes. The ICD at this point will be recoded as 790 metres (same procedure used to censor cases in AWD will be applied for the ICD)
- The proportion of patients who improved AWD at each time point by
  - 60 metres or more from baseline
  - 100 metres or more from baseline
- The proportion of who improved ICD at each time point by
  - 60 metres or more from baseline
  - 100 metres or more from baseline
- Quality of life scores measured at baseline, 3, 6 and 12 months
  - Recorded ICQ Health score (calculated using the formula in Appendix 2 - Section 13.2.1)
  - Recorded EQ-5D-5L Health state score [7]

Imperial Clinical Trials Unit	STATISTICAL ANALYSIS PLAN	NESIC
-------------------------------	---------------------------	-------

- Short Form 36 (SF-36) scores (Using Health Outcome Scoring Software 4.0 see section 13.2.2) [8]

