	ICQ health score (calculated using the formulas in Appendix 2 measured at 3, 6 and 12 months	Plot of mean ICQ health score change over time by treatment arm (mean and SD). ANCOVA model for ICQ health score on treatment group indicator, controlling for ICD baseline measurement.
	EQ-5D-5L health score measured at 3, 6 and 12 months	Plot of mean EQ-5D-5L health score changes over time by treatment arm (mean and SD). ANCOVA model for EQ-5D-5L health score on treatment group indicator, controlling for EQ-5D-5L baseline measurement.
	SF36-scores (obtained using software Appendix 2) measured at 3, 6 and 12 months	Plot of mean SF36-scores change over time by treatment arm (mean and SD).
	Section scores Physical function score Role-Physical score Body pain score General Health score Vitality score Social functioning score Role-Emotional score Mental Health score	Separate ANCOVA models for SF36 scores on treatment group indicator, controlling for the baseline measurement of the outcome being analysed.
	Summary scores Physical component scores (PCS) Mental component scores (MCS)	
	Haemodynamic AssessmentT	
	Duplex ultrasonography measure at baseline and 3 months • Mean Volume Flow (VF, cc/min) for one leg (either Right or Left) for each patient • Mean Time average Mean Velocity (TAMV, cm/s) one leg (Left or Right) 2 models	Separate Linear regression models for the Duplex ultrasonography measurements (MVF and MTAMV), using as covariates: Specific baseline measurement Treatment Time Time*Treatment interaction Centre Group (SET vs non-SET) Age Gender BMI
	Laser Doppler Flowmetry (LDF) measure at baseline, 3, 6 and 12 months • Mean Blood flux for one leg (Left or Right)	Separate ANCOVA models for the variables of Laser Doppler Flowmetry (LDF) on treatment group indicator, controlling the baseline measurement of the outcome being analysed.
	Ankle Brachial Pressure Index (ABPI) measure at baseline, 3, 6 and 12 months ABPI for the Left Ankle ABPI for the Right Ankle	Separate ANCOVA models for the variables of Ankle Brachial Pressure Index (ABPI) on treatment group indicator, controlling the baseline measurement of the outcome being analysed.

Compliance with interventions		

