### **8.3 Secondary End Points Analysis**

#### **8.3.1 Continuous Secondary End Point Analysis**

The continuous variables of initial claudication distance (ICD), measured at baseline, 3, 6, and 12 months will be analysed using a Multilevel Tobit model fitted to the censored ICD measurements. The Multilevel Tobit models will be performed to investigate the effect of the treatment indicator on the changes over time (3, 6, and 12 months), treating patient as a random effect, while the baseline measurement of the continuous ICD variable, treatment, time, interaction of time\*treatment, centre, group (SET vs non-SET), age, gender and BMI will be treated as covariates. Results of the Multilevel Tobit model will be presented (see Table 24 Section 8.9.6.1).

A summary table of proportion of patients who increased the ICD both by more than 60 and by more than 100 metres by treatment and by visit will be presented (Table 25 and Table 26)

The secondary end points concerned with quality of life scores (QoL) measured at baseline, 3, 6 and 12 months, will be analysed using separate ANCOVA models for each outcome variable. The measurements of quality of life are the Intermittent Claudication Questionnaire (ICQ), EuroQoL 5D 5L (EQ-5D-5L) and the SF-36.

The ANCOVA models of each of the QoL scores will be performed to investigate changes in QoL over time and to assess the difference between the two treatment groups, while controlling for the baseline measurement of the QoL score being analysed. Results of the ANCOVA models will be presented in tables (see Section 8.9.6.2).

All individual scores for ICQ, EuroQoL 5D 5L and the SF-36 will be presented as Plots. Plots of the mean QoL scores will be used to illustrate changes over time by treatment arm (Figure 1-3, Section 8.10).

Duplex ultrasonography (DU) measurements (Mean Volume Flow and Mean Time Average Mean Velocity) from the Haemodynamic assessment will be analysed using separate linear regression models. The linear regression models will be used to compare the Mean Volume Flow (VF) and Mean Time Average Mean Velocity (TAMV)

Imperial Clinical Trials Unit	STATISTICAL ANALYSIS PLAN	NESIC
-------------------------------	---------------------------	-------

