#### 8.9.4 Derived Variables

**Table 13 Summary of ICQ and EQ-5D-5L - Quality of Life scores of randomised patients (ITT) by treatment**

QoL	Specific Score, mean(SD)	Treatment  : NMES + EA and NMES+EA+SET N=(XX)	Control  : EA and EA+SET N=(XX)	Total N=(XX)
ICQ*	ICQ health score			
	Baseline	XX.XX (XX.XX)	XX.XX (XX.XX)	XX.XX (XX.XX)
	12 weeks	XX.XX (XX.XX)	XX.XX (XX.XX)	XX.XX (XX.XX)
	6 months	XX.XX (XX.XX)	XX.XX (XX.XX)	XX.XX (XX.XX)
	12 months	XX.XX (XX.XX)	XX.XX (XX.XX)	XX.XX (XX.XX)
EQ-5D-5L	Health state score			
	Baseline	XX.XX (XX.XX)	XX.XX (XX.XX)	XX.XX (XX.XX)
	12 weeks	XX.XX (XX.XX)	XX.XX (XX.XX)	XX.XX (XX.XX)
	6 months	XX.XX (XX.XX)	XX.XX (XX.XX)	XX.XX (XX.XX)
	12 months	XX.XX (XX.XX)	XX.XX (XX.XX)	XX.XX (XX.XX)

\*The scores of ICQ where obtained using the procedure described in Appendix 2

Treatment: NMES + Local Available Exercise Therapy (NMES+EA and NMES+EA+SET)

Control: Local Available Exercise Therapy (EA and EA+SET)

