**Table 26 Summary of Proportion of Patients that improved ICD by more than 100 m by visit and by treatment.**  
**Same display as Table 25, but for the Proportion of Patients that improved ICD by more than 100 m**

### 8.9.6.2 Quality of Life scores

See Table 13 and 14 for Summary of Quality of life scores by time point and treatment.

**Table 27 Output of ANCOVA model for changes in Intermittent Claudication score (ICQ-score) from baseline to follow up periods (3,6 and 12 months)**

Source	Partial SS	df	MS	F	Prob>F
Model	XX.XX	XX.XX	X.XX	X.XXX	X.XX
Treatment group indicator	XX.XX	XX.XX	X.XX	X.XXX	X.XX
Baseline measurement	XX.XX	XX.XX	X.XX	X.XXX	X.XX
Residual	XX.XX	XX.XX	X.XX		
Total	XX.XX	XX.XX	XX.XX		
Residual	XX.XX	XX.XX	X.XX	X.XXX	X.XX

**Table 28 Output of ANCOVA model for changes in Quality of life (EQ-5D-5L score) between baseline and follow up periods (3,6 and 12 months).** Same display as Table 27, but for the Quality of life (EQ-5D-5L score). ANCOVA model: Quality of life (EQ-5D-5L score) at 3,6 and 12 months = intercept + treatment group indicator + EQ-5D-5L score (Baseline). Treatment=NMES + local available exercise therapy vs. local available exercise therapy only (1,0).

**Table 29 Output of ANCOVA model for changes in Quality of life (SF-36-score) - Physical function score. between baseline and follow up periods (3,6 and 12 months).** Same display as Table 27, but for the Physical function score from the SF-36 questionnaire. ANCOVA model: Physical function score (SF-36-score) at 3,6 and 12 months = intercept + treatment group indicator + Physical function (Baseline). Treatment=NMES + local available exercise therapy vs. local available exercise therapy only (1,0).

**Table 30 Output of ANCOVA model for changes in Quality of life (SF-36-score) – Role Physical score between baseline and follow up periods (3,6 and 12 months).** Same display as Table 27, but for Role Physical score from the SF-36 questionnaire. ANCOVA model: Role Physical score (SF-36-score) at 3,6 and 12 months = intercept + treatment group indicator + Role Physical score (Baseline). Treatment=NMES + local available exercise therapy vs. local available exercise therapy only (1,0).

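### SAP Table A4 scores moderate leg pain worse than severe leg pain on ICQ question 1, and the Table 2 ICQ row names baseline ICD instead of baseline ICQ

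*SAP*

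**What the plan says.** The ICQ score is defined in SAP section 13.2.1. It is "obtained by adding all the points assigned in each question and scaling to 100", with a maximum of 80. The points are in Table A4, which sets two answer lists side by side. The left list is question 1 and the right list is questions 2–8. The rows at issue are "Severe 3 Very limited 3.75" followed by "Moderate 4 Totally limited 5". Read down the left side, question 1 is scored None 0, Very mild 1, Mild 2, Severe 3, Moderate 4, Very severe 5.

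The rest of the SAP relies on this appendix. Section 7.4 lists "Recorded ICQ Health score (calculated using the formula in Appendix 2 - Section 13.2.1" among the secondary endpoint variables. The ICQ row of Table 2 also points to Appendix 2, and the footnote to Table 13 says "The scores of ICQ where obtained using the procedure described in Appendix 2".

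On the analysis model, the Table 2 ICQ row specifies "ANCOVA model for ICQ health score on treatment group indicator, controlling for ICD baseline measurement". Section 8.3.1 describes the models for all quality-of-life scores, ICQ included, as assessing the treatment difference "while controlling for the baseline measurement of the QoL score being analysed".

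**The concern.** The words themselves show that the scoring is out of order: severe pain should not score between mild and moderate. If the derivation is programmed from the table, the transposition enters ICQ at baseline and at 3, 6 and 12 months, so it affects both the outcome and the baseline covariate.

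ICQ is the trial's disease-specific quality-of-life measure. The error would run through both the ITT and the per-protocol analyses. The complete-case versus imputed comparison (8.6.2.3), the complier analysis (8.8.1) and the remote-collection analysis (8.8.2) would all use the same scores, so none of them would reveal it.

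The covariate point is separate and smaller. ICD (initial claudication distance) is a treadmill measure, not the ICQ. Taken literally, Table 2 and section 8.3.1 give two different ANCOVA models for the same endpoint.

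**Working it through.** **Reproducing the stated maximum.** Table A4 covers question 1, questions 2–8, question 9 and questions 10–16, which is 1 + 7 + 1 + 7 = 16 items. Each has a top score of 5, and 16 × 5 = 80, as section 13.2.1 states. Swapping two labels inside question 1 leaves the maximum at 80, so a range check would not detect the problem. One raw point is 100/80 = 1.25 on the reported scale. Question 1 carries 5/80 = 6.25% of the total.

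**Printed against ordered scores for question 1.** A higher score is worse.

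| Answer | Printed | In order of severity | Error on 0–100 scale |
|---|---|---|---|
| None | 0 | 0 | 0 |
| Very mild | 1 | 1 | 0 |
| Mild | 2 | 2 | 0 |
| Moderate | 4 | 3 | +1.25 |
| Severe | 3 | 4 | −1.25 |
| Very severe | 5 | 5 | 0 |

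**Effect on change scores.** Six answers give 15 possible improvements. Six of these involve neither Moderate nor Severe and are scored correctly. The other nine are not:

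- Severe to Moderate reverses sign: (4 − 3) × 1.25 = +1.25 as printed, against (3 − 4) × 1.25 = −1.25 in order, an error of +2.5.
- Four are understated by 1.25: Severe to None, to Very mild or to Mild, and Very severe to Moderate.
- Four are overstated by 1.25: Moderate to None, to Very mild or to Mild, and Very severe to Severe.

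These are counts of possible transitions, not of patients. The documents do not give the distribution of answers.

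**Between-arm effect at a visit.** Let pM and pS be the proportions answering Moderate and Severe. The error in the difference between arms is 1.25 × [(pM − pS) in NMES − (pM − pS) in control]. Assumed cases:

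- Same mix in both arms: 0.
- 10 percentage points more NMES patients move from Severe to Moderate: 2.5 × 0.10 = +0.25.
- 10 percentage points more move from Moderate to Mild: −1.25 × 0.10 = −0.125.
- The same two cases at 25 percentage points: 2.5 × 0.25 = +0.625 and −1.25 × 0.25 = −0.3125.

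A positive error works against NMES and a negative one works for it. Real data would mix these changes, so they partly cancel and the net direction cannot be known in advance.

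**The covariate.** In Table 2 the EQ-5D-5L and SF-36 entries use their own baselines, and so do the output shells in Tables 28–38. Table 27, "Output of ANCOVA model for changes in Intermittent Claudication score (ICQ-score) from baseline to follow up periods (3,6 and 12 months", has an unnamed baseline row. Randomisation keeps the treatment estimate free of bias with either covariate. The loss is in precision, with standard-error ratio √[(1 − r²ICD)/(1 − r²ICQ)], where r is the correlation of each baseline with follow-up ICQ. The documents give no correlations. Assuming 0.3 for ICD and 0.6 for ICQ, the ratio is √(0.91/0.64) = 1.19. It ranges from √(0.8775/0.75) = 1.08 (0.35 and 0.5) to √(0.96/0.51) = 1.37 (0.2 and 0.7). It is 1, no loss, if section 8.3.1 is followed.

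**The case against.** The strongest reply concerns size. The fault touches one item of 16, moves an affected score by 1.25 points in 100, and sits on a secondary endpoint. Section 13.2.1 also refers to the questionnaire itself and cites its source, so the data may have been captured with the correct codes. If the database stores answer position, nothing changes. All of this stands, and it is why the point does not threaten the trial's main result. It does not make the table right: Table A4 is the only item scoring the SAP prints, and the documents do not show how question 1 was coded.

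A fault in reading the PDF is possible in principle. It is unlikely, because the scores 0 to 5 and the neighbouring list in the same rows are in order. The final codes should still be confirmed against the instrument, which was not available for this review.

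On the covariate, the intended reading is fairly clear from section 8.3.1 and the sibling tables. ICD is one letter away from ICQ, and a typing slip is the likely explanation. The standard-error figures rest wholly on assumed correlations and are illustrative only.

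**Conclusion.** The concern holds. Followed literally, the SAP's scoring rule gives wrong ICQ scores for every patient-visit answered Moderate or Severe on question 1. Each error is 1.25 points on the 0–100 scale, and a severe-to-moderate improvement is recorded as a worsening. The plausible between-arm shift is well under one point, of unknown sign, and depends on answer proportions assumed here. Whether any score is affected depends on the database coding.

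The Table 2 covariate is a real inconsistency with a clear intended reading, and it costs at most precision and protection against chance imbalance in baseline ICQ. Absolute walking distance at 3 months and the sample size are unaffected. The corrections should be made because they cost almost nothing and because anyone reproducing ICQ from the SAP could get different numbers from the trial team.

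**What to change.** 1. Check the question 1 codes against the source cited in section 13.2.1 and against the response coding in the database.
2. If the check confirms the order that the labels imply, print Moderate = 3 and Severe = 4 in Table A4.
3. If any ICQ scores were computed from the printed labels, re-derive them at all four visits and re-run the ICQ analyses.
4. In the ICQ row of Table 2, replace baseline ICD with baseline ICQ, and name baseline ICQ in the Table 27 shell as Tables 28–38 do for their own scores.

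The cost is two text corrections, one table label and one coding check. The ICQ derivation is repeated only if step 3 applies.
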